6. The recording of randomization in IWRS of a participant who is eligible for intervention must be repeated on the day of the planned start of intervention. This will be considered as confirmation of randomization and will trigger the notification to the site about the study medication assignment.
7. The first dose of study intervention will be administered only after the 24h cough recording has been completed and the eligibility of the participant has been confirmed.
8. PK sampling timing: at Visit 2 and Visit 6: pre-dose, 2 hours and 4 hours post-dose; at Visit 4 and Visit 5: 6 hours post-dose (± 15 min time window allowed for all samples). More details on PK sampling and collection of information about the type of meal taken in timely relation to PK sampling and drug intake are provided in Section 8.5.
9. At TV, sparse PK sampling will not be conducted.
10. The sample has to be taken prior to the start of study intervention.
11. At TV, biomarker sampling will not be conducted.
12. Blood sampling for genetics will have to be taken on Day 0 of Visit 2.
13. Height will be measured at Visit 1 only.
14. Blood pressure measurements can be repeated once during the screening visit if medically justified (e.g. in order to avoid suspected "white-coat hypertension").
15. Hematology, chemistry and coagulation tests are to be conducted at a central laboratory every 4 weeks.
16. An oropharyngeal swab sample must be collected for quantitative measurement of the virus and a serum sample for the measurement of antibodies.
17. Pregnancy testing will be only applicable for women of childbearing potential. A serum test will be performed at screening and urine testing will be performed at all other site visits.
18. Spirometry results must not be older than 3 months prior to screening.
19. Adverse events will be collected from signing the informed consent until the follow-up visit at the time points specified in the SoA.
20. If a participant does not show up at the site for the planned safety follow-up visit, the survival status has to be checked.
21. Recording of cough with the cough recording device worn by participant for 24 hours.
22. Recording of data about cough severity on SCCD by participant every day on a handheld device.
23. Cough Severity VAS will be completed by the participant every day on a handheld device.
24. LCQ, EQ-5D-5L, PGI-S, and PGI-C will be completed by the participant on a tablet device during the study visits.

2. Introduction

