4.1.1 Pre-Intervention Period

Written informed consent form must be obtained before any study related activities are performed. After providing the written informed consent, participants will undergo a screening evaluation to determine their eligibility. The screening evaluation will take place on Day -14 before Visit 2.

The screening of each participant has to be recorded in the IWRS system. To assure timely drug supply to each study site, the recording of randomization must be completed at least 1 day but not later than 4 days after Visit 1 (before Visit 2). The recording of randomization in IWRS of a participant who is eligible for intervention must be repeated on the day of the planned start of intervention. This will be considered confirmation of randomization and will trigger the notification to the site about the study intervention assignment.

Following screening, eligible participants will be randomized to one of four parallel intervention groups of BAY 1817080.

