5.2 Exclusion Criteria

Participants are excluded from the study if any of the following criteria apply:

RUCC-related Medical Conditions

1. Smoking history within the last 12 months before screening (all forms of smoking, including e-cigarettes, cannabis and others), and any former smoker with more than 20 pack-years.
2. Ongoing or previous exposure to inhalational toxic fumes (e.g., ammonia, chlorine, nitrogen dioxide, phosgene and sulfur dioxide) within the last 12 months before screening.
3. Chest radiograph or CT within the last 24 months before screening and subsequent to the onset of chronic cough with presence of any obvious lung disease that could be responsible or contributing for the cough (e.g., bronchiectasis, cavitory lesions, interstitial pulmonary fibrosis, pneumothorax, pleural disease, unstable rib fracture, tuberculosis).

4. Forced expiratory volume in 1 second (FEV₁)/ Forced vital capacity (FVC) ratio < 60% or a history of frequent exacerbations of chronic obstructive pulmonary disease (COPD).
5. Respiratory tract infection within 4 weeks before screening.
6. History of chronic bronchitis.
7. Active state of massive hemoptysis⁵ or pulmonary hemorrhage, including those events managed by bronchial artery embolization or any history of bronchial artery embolization or massive hemoptysis within 3 months prior to screening.

Hepatic-related criteria

8. Moderate-to-severe hepatic impairment defined as Child-Pugh Class B or C.
9. ALT >2xULN, or AST >2xULN, or total bilirubin greater than ULN, or alkaline phosphatase (AP) >2x ULN, or INR greater than ULN (unless related to anticoagulation treatment).

Renal-related criteria

10. Estimated glomerular filtration rate (eGFR) <30 mL/min/1.73 m² calculated by Modification of Diet in Renal Disease (MDRD) formula.

Different eGFR formulas will be used for participants enrolled at sites in Japan in this study (for more details, see Section 10.6).

General Medical Conditions

11. Systolic blood pressure \geq 160 mmHg and/or diastolic blood pressure \geq 100 mmHg at screening visit.
12. Any other diseases or conditions that according to the investigator can compromise the function of the body systems and could result in altered absorption, excessive accumulation, impaired metabolism, or altered excretion of the study intervention (e.g., chronic bowel disease, Crohn's disease and ulcerative colitis).
13. Esophageal achalasia.

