#### **4.5.5 Cough Severity VAS and SCCD**

VAS and SCCD are collected on a daily basis from Visit 1 until the Safety Follow-up Visit.

The baseline value is calculated as the average of the 14 days up to and including Visit 2, i.e. the average of day -13 up to day 0.

The value at a post-baseline visit is calculated analogously as the average of the 14 days up to and including the respective visit.

If there are less than 14 days between consecutive visits, the average will only be taken over the days between the visits and including the respective visit.

If there are less than 8 out of 14 days available, the value will be set to missing [3]. The VAS reported for the day of Visit 1 will not be considered at all for statistical analyses, as it has a different recall period.

For the SCCD item-levelscore calculation rules see Psychometric SAP v3.0. [4]. Missing data will not be imputed.

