#### **4.5.8 Definition of Treatment-emergence**

A treatment-emergent AE is defined as any event arising or worsening after the start of study drug administration until 14 days after the last study medication intake.

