## 6.2 Efficacy

### 6.2.1 Primary Efficacy Endpoint

The primary efficacy **variable** is the change from baseline in 24h cough count after 12 weeks of intervention. Baseline is defined as the measurement at Visit 2. The raw 24h cough count will be standardized to an average hourly count, and then log-transformed for the analysis due to the expected range and distribution of the data. After applying a log-transformation, the data are expected to be normally distributed.

The data will be log-transformed first, before calculating any group means or changes from baseline, i.e. the observation of participant  $i$  at visit  $j$ ,  $x_{ij}$  will be transformed into  $y_{ij} = \log(x_{ij})$  with  $\log(\cdot)$  being the natural logarithm. All inferential statistics and modelling will

be based on the log-transformed observations  $y_{ij}$ . However, for easier interpretation of the magnitude of effects, the display of the results will focus on values on the original scale.

This results in display of geometric means for observations obtained at specific visits as

$$\begin{aligned} \exp(\bar{y}_j^{arith}) &= \exp\left(\frac{1}{n} \sum_{i=1}^n y_{ij}\right) \\ &= \exp\left(\frac{1}{n} \sum_{i=1}^n \log(x_{ij})\right) = \exp\left(\frac{1}{n} \log \prod_{i=1}^n x_{ij}\right) = \exp\left(\log \sqrt[n]{\prod_{i=1}^n x_{ij}}\right) = \bar{x}_j^{geo} \end{aligned}$$

where  $\bar{y}_j^{arith}$  and  $\bar{x}_j^{geo}$  denote arithmetic and geometric means, respectively.

Similarly, for the change from baseline, the arithmetic mean of the difference on the log scale translates into the ratio of geometric means on the original scale:

$$\begin{aligned} \exp(\bar{y}_{chg}^{arith}) &= \exp\left(\frac{1}{n} \sum_{i=1}^n (y_{ij} - y_{i,BL})\right) = \exp(\bar{y}_j^{arith} - \bar{y}_{BL}^{arith}) \\ &= \exp\left(\log(\bar{x}_j^{geo}) - \log(\bar{x}_{BL}^{geo})\right) = \exp\left(\log\left(\frac{\bar{x}_j^{geo}}{\bar{x}_{BL}^{geo}}\right)\right) = \frac{\bar{x}_j^{geo}}{\bar{x}_{BL}^{geo}} \end{aligned}$$

For ease of interpretation, in addition to the ratio of geometric means, the relative change (of geometric means) in % will be displayed as

$$\bar{x}_{rel\ chg} = \left(\frac{\bar{x}_j^{geo}}{\bar{x}_{BL}^{geo}} - 1\right) * 100\% = \frac{\bar{x}_j^{geo} - \bar{x}_{BL}^{geo}}{\bar{x}_{BL}^{geo}} * 100\%.$$

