### 6.2.1.3.4 Accounting for respiratory tract infections

To account for the possible impact of respiratory tract infections on cough count, the primary analysis will be repeated on the subpopulations of patients in the PPS with and without a treatment-emergent AE belonging to the MedDRA HLTG "Respiratory tract infection", to the HLTG "Upper respiratory tract infections" or to the HLTG "Lower respiratory tract and lung infections".

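### The respiratory-infection sensitivity analysis leaves participants with an infected baseline recording in its no-infection subset

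*Protocol*

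**What the plan says.** - Protocol 5.2, criterion 5, excludes a "Respiratory tract infection within 4 weeks before screening". No criterion names a respiratory infection between screening and the first dose, apart from the separate SARS-CoV-2 tests at screening.
- Protocol 4.1.1: "The screening evaluation will take place on Day -14 before Visit 2". The schedule of activities gives 14 to 16 days.
- SAP 6.2.1, for the cough count: "Baseline is defined as the measurement at Visit 2".
- SAP 6.2.1.3.4 addresses the effect of respiratory infections by repeating the primary analysis in per-protocol participants "with and without a treatment-emergent AE belonging to the MedDRA HLTG" for respiratory tract infections.
- SAP 4.5.8 defines treatment-emergent as "any event arising or worsening after the start of study drug administration until 14 days after the last study medication intake".
- Notes to the schedule of activities: "Adverse events will be collected from signing the informed consent until the follow-up visit". SAP 6.4.1 tabulates pre-treatment events separately and descriptively.
- COVID-19 has its own rule (SAP 4.5.3 and 6.2.1). Efficacy data are discarded from the start of infection, and no first-dose limit is stated.
- The cough severity VAS and cough diary baselines are "the average of day -13 up to day 0", and the Leicester Cough Questionnaire at Visit 2 has a two-week recall. These baselines lie in the same interval, but SAP 6.2.1.3.4 repeats only the primary analysis.

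**The concern.** The infection exclusion ends at screening, but the baseline that enters every cough-count change score is recorded about two weeks later. A participant who catches an ordinary cold a few days before Visit 2 still satisfies criterion 5 as worded. The protocol's introduction describes infection-related cough as short-lived and usually self-limiting. Cough would then fall after baseline in any arm, and the fall would look like improvement.

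The sensitivity analysis written to deal with infections does not catch this. It finds infections that begin or worsen after the first dose, which push post-baseline cough up. It does not find infections that were present at baseline and then cleared, which push the change score down. The subset meant to be free of infection has therefore been cleaned on one side only. Within-arm ratios to baseline are at stake, and the SAP makes these its population-level summary.

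**Working it through.** **The plan's own figure.** Inputs from Protocol 9.2 and Table 9-1: 50 evaluable per arm, SD 0.8 on the log scale, one-sided alpha 0.10, four candidate models. The maximum-contrast test has a multiplicity-adjusted critical value of 1.481. Simulated power is 84.6% (Emax 1), 85.0% (Emax 2), 88.9% (sigmoidal 1) and 91.3% (sigmoidal 2). This agrees with the stated minimum of 85% to within simulation and rounding. Likewise 200/0.85 = 235.3, which rounds up to 236.

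**Where a participant is placed.** Take an infection that starts on Day -3 and resolves without worsening.

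| Step | Rule | Result |
|---|---|---|
| Eligibility | Criterion 5 looks back 4 weeks from screening | Not excluded by it |
| Baseline | Visit 2 recording, Day -1 to Day 0 | Taken during the infection |
| Safety data | Events collected from consent | Recorded, tabulated as pre-treatment |
| SAP 6.2.1.3.4 | Treatment-emergent events only | No-infection subset |

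**Size.** The documents give neither the share affected, p, nor the factor f by which cough is raised at baseline. I assume p = 2-10% and f = 1.25-2, with full resolution afterwards. For orientation, 0.5 to 2 infections per person-year (also assumed) over 16 days gives 16/365 x 0.5 = 2.2% to 16/365 x 2 = 8.8%, or 5 to 21 of 236. That is an upper range, because some of these infections would be over by Visit 2.

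- False change in one affected participant: 1/f - 1, which is -20% at f = 1.25 and -50% at f = 2. A participant with no true change counts as a 30% responder once f reaches 1/0.7 = 1.43.
- Shift in an arm's mean log change: -p x ln(f). Smallest: -0.02 x 0.223 = -0.0045 (-0.4%). Largest: -0.10 x 0.693 = -0.069 (-6.7%). Against the assumed placebo change of -0.19, that is 0.0045/0.19 = 2% to 0.069/0.19 = 36%.

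These shifts apply where no later infections offset them, which is the situation in the no-infection subset, with p read as the share within it.

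**Effect on the primary test.**

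- Expected shift between arms: zero, because participants are randomised and the contrasts sum to zero.
- Chance imbalance between two arms: ln(f) x sqrt(2p(1-p)/50), from 0.006 to 0.042. The standard error of an arm difference is 0.8 x sqrt(2/50) = 0.16.
- Inflated SD: sqrt(0.64 + p(1-p) x ln(f)^2), at most sqrt(0.64 + 0.09 x 0.480) = 0.827. Minimum power falls from 84.6% to 82.9% in that worst case.
- Simulated ANCOVA with no drug effect and 5% or 10% of baselines doubled: the adjusted placebo change moved by about -0.03 or -0.07, so adjusting for baseline does not remove the shift. The 150 mg minus placebo difference stayed at about 0. Type I error was 9.8% and 9.6%, and a repeat with the test pointed in the direction of benefit also gave about 10%.

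**The case against.** The strongest reply is that little of this reaches the main analysis. Infections also occur around Week 12, where they raise cough and work the other way. Criterion 5 arguably makes the baseline cleaner than Week 12, so over the whole per-protocol set the net effect could be nil or even towards less improvement. This stands. It is why the point is confined to the no-infection subset, where the offsetting infections have been taken out.

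Some safeguards exist. Eligibility is confirmed after the baseline recording. Exclusion 14 covers unstable conditions that could affect interpretation, and Protocol 2.3.3.7 says participants with symptoms suggestive of COVID-19 will not be included. Suspected COVID-19 is one of the terms that trigger the SAP's discard rule, and an infection that worsens on treatment does count as treatment-emergent. The separate validity specifications for the per-protocol set may also list such infections; that document is not available. These safeguards narrow the gap, but in the text at hand none of them links an ordinary respiratory infection to the baseline recording.

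A reader might infer more than the documents support:

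- That these infections go unrecorded. They are collected from consent and tabulated.
- That the dose-response test is biased or the log-scale dose differences diluted. An equal shift in all arms cancels in the contrasts.
- That VAS responders would be created in the same way. With onset on Day -3, only 4 of the 14 averaged days are affected, so a 30-unit rise in the mean would need 30 x 14/4 = 105 units a day on a 0-100 scale.

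**Conclusion.** The point holds in a narrow form. Non-COVID respiratory infections starting between screening and the Visit 2 recording fall outside criterion 5 and are used in no efficacy analysis. SAP 6.2.1.3.4 places affected participants in its no-infection subset unless the event worsens or another infection follows. The within-arm ratios to baseline in that subset can be tilted towards improvement by about -0.005 to -0.07 log units. That range rests entirely on the assumed 2-10% affected, the 1.25- to 2-fold inflation and full resolution. The primary dose-response test keeps its type I error and loses at most about two points of power under the most extreme of these assumptions. This is a cheap improvement to one sensitivity analysis. It does not threaten the primary conclusion.

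**What to change.** In SAP 6.2.1.3.4, extend the infection flag beyond treatment-emergent events. Include any respiratory-infection adverse event collected from consent whose dates overlap the Visit 2 recording, so that the no-infection subset excludes these participants. Where dates are incomplete, treat an event as overlapping if it could have done so, in line with the worst-case approach in SAP 4.3.1.2.

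Optionally, add a version that keeps flagged participants and uses their Visit 1 24-hour recording as the cough-count baseline, provided it has at least 20 valid hours and precedes the onset of infection.

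The data are already collected, and SAP 4.6 provides for amendments or supplements. The cost is a little programming, a slightly smaller no-infection subset and, in the optional version, a baseline about two weeks older for a few participants. It should be written before unblinding.

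I would not extend the window of criterion 5. The protocol amendment reports unexpectedly rapid recruitment, so few participants may be left for a change to reach. Randomisation is recorded 1 to 4 days after Visit 1, so late exclusions would become dropouts who are not replaced and who stay in the full analysis set.

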5.3 Lifestyle Considerations

All forms of smoking, including e-cigarettes, cannabis and others, are not allowed. Use of tobacco products will not be allowed from screening until after the final SFU visit.

As a precautionary measure, excessive exposure to sunlight should be avoided during the intervention period. Participants will be advised to use conventional ultraviolet (UV) sunscreens, to avoid prolonged sunbathing especially when traveling to a different geographical area with greater sunshine, to avoid the use of solarium and also to wear sunglasses if exposed to direct or excessive sunlight (see Section 2.3.3.6).

5.4 Screen Failures

Screen failures are defined as participants who consent to participate in the clinical study but are not subsequently randomized to study intervention. A minimal set of screen failure information is required to ensure transparent reporting of screen failure participants to meet the Consolidated Standards of Reporting Trials (CONSORT) publishing requirements and to respond to queries from regulatory authorities. Minimal information includes

- Demography,
- Reason for screen failure,
- Eligibility criteria, and
- Date of last visit.

A participant who, for any reason (e.g., failure to satisfy the selection criteria), terminates the study before the time point used for the definition of “dropout” (see below) is regarded a “screening failure”.

Re-starting the defined set of screening procedures to enable the “screening failure” patient’s participation at a later time point is not allowed.

Dropout

A participant who discontinues study participation prematurely for any reason is defined as a “dropout” if the participant has already been randomized to study intervention. Dropouts will not be replaced.

6. Study Intervention

Study intervention is defined as any investigational intervention(s), marketed product(s), placebo, or medical device(s) intended to be administered to a study participant according to the study protocol.

6.1 Study Interventions Administered

- Each participant will be randomized to receive one of three oral doses of BAY 1817080 or placebo, administered twice daily
- Participants should be instructed to take the morning dose of study intervention at approximately the same time of day, every day over the course of 12 weeks. The interval between the application of the morning and the evening dose should be with an interval of approximately 12 hours.
- The morning dose should be taken at the site on the second day of Visit 6 (see also Section 8.5)
- Tablets are not to be broken, halved or crushed; they should be swallowed as a complete unit with water.
- Tablets can be taken with or without food. See Section 8.5 for detailed instructions regarding recording of the drug intake and the food intake before or after the drug intake in relation to blood sampling for PK.
- Participants will have to confirm the tablet intake twice per day by reporting this on the handheld device. In addition, the time of the tablet intake will be collected.
- If a dose of study intervention has been missed:
 - If ≤ 6 hours has passed since the dose was due, it should be taken immediately
 - If > 6 hours have passed since the dose was due, the dose should be skipped and the next dose should be taken according to the regular schedule.

Table 6–1: Study Interventions Administered

	BAY 1817080	Placebo
Intervention Name	BAY 1817080	Placebo for BAY 1817080
Type	Drug	Placebo
Dose formulation	Tablet	Tablet
Unit dose strengths	25 mg and 100 mg	NA (Placebo for BAY 1817080 25 mg and BAY 1817080 100 mg)
Dosage Levels	25 mg or 75 mg or 150 mg BID	NA (Placebo)
Route of Administration	Oral	Oral
Packaging and Labeling	Tablets will be provided in blisters. Study intervention will be labeled as required per country requirement.	

Abbreviations: BID = twice daily; NA = not applicable

6.1.1 Medical Device

A commercially available cough recording device (VitaloJAK™; Vitalograph GmbH) will be used for the 24-hour ambulatory measurements. For further information, see the handling instruction and the instruction manual as provided with the device by the legal manufacturer.

6.2 Preparation/Handling/Storage/Accountability

The investigator or designee must confirm that appropriate temperature conditions, if applicable, have been maintained during transit for all study interventions received and any discrepancies are reported and resolved before use of the study intervention.

Only participants enrolled in the study may receive the study intervention and only authorized site staff may supply or administer the study intervention.

All study interventions must be stored in a secure, environmentally controlled, and monitored (manual or automated) area in accordance with the labeled storage conditions with access limited to the investigator and authorized site staff.

The investigator, institution, or the head of the medical institution (where applicable) is responsible for study intervention accountability, reconciliation, and record maintenance (i.e., receipt, reconciliation, and final disposition records).

Further guidance and information for the final disposition of unused study interventions are provided in the Investigator Site File.

Study interventions will be dispensed at the visits summarized in SoA. Returned study interventions must not be re-dispensed to the participants.

